7.1. Secondary Efficacy Analyses

7.1.1. Endpoint / Variables

- Proportion of participants with Plasma HIV-RNA < 50 copies/mL and plasma HIV-1 RNA ≥ 50 c/mL, respectively, over time using the FDA Snapshot Algorithm. See Section 13.9 for Snapshot Algorithm details.

Other secondary efficacy endpoints:

- Proportion of participants with confirmed virologic failure (CVF) over time
- Absolute values and changes from Baseline CD4+ cell count over time

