7.1.3. Strategy for Intercurrent (Post-Randomization) Events

- Participants with last available HIV-1 RNA measurement less than 50 copies/mL while the participant is on treatment within the analysis visit window of interest are classified as HIV-1 RNA < 50 c/mL. Participants without evaluable HIV-RNA data for the visit of interest or who change treatment not permitted per protocol before the analysis window are considered non-responders.
- Participants with last available HIV-1 RNA measurement greater or equal to 50 copies/mL while the participant is on treatment within the analysis visit window of interest are classified as HIV-1 RNA ≥ 50 c/mL. Participants without evaluable HIV-RNA data for the visit of interest and who discontinue treatment for reasons not related to adverse event while having HIV-1 RNA ≥ 50 copies/mL at time of

discontinuation or who change study treatment not permitted per protocol before the analysis window are also classified as having HIV-RNA ≥ 50 copies/mL.

Missing viral load values for reasons related to COVID-19 issues (e.g. participant is unable to have viral load assessed due to barriers in attending the clinic during the pandemic or COVID-19 related adverse events leading to treatment discontinuation) will be imputed using an LOCF approach in which the last on-treatment viral load value will be carried forward and used in place of missing values.

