7.1.4.1. Statistical Methodology Specification

Endpoint / Variables

• Proportion of participants with plasma HIV-1 RNA < 50 c/mL over time using the FDA Snapshot algorithm (Safety population)• Proportion of participants with plasma HIV-1 RNA ≥ 50 c/mL over time using the FDA Snapshot algorithm (Safety population)
Results Presentation

• The proportion of participants with HIV-1 RNA < 50 c/mL and HIV-1 RNA ≥ 50 c/mL, respectively, at each planned visit with corresponding 95% confidence intervals calculated using the Clopper-Pearson exact method.• The proportion of participants in each Snapshot study outcome category and sub-category will be summarized at Month 12, in which default sub-categories have been expanded to present COVID-19 vs. non COVID-19 related impact (as described in Section 13.9).

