13.6.3. Efficacy

Efficacy	
Snapshot	

 • The Snapshot algorithm is intended to be primarily a virologic assessment of the endpoint, and as such follows a "virology first" hierarchy. • 'HIV-1 RNA < 50 c/mL' or 'HIV-1 RNA ≥ 50 c/mL' within an analysis window (see Table 2 and Table 3) is typically determined by the last available HIV-1 RNA measurement in that window while the participant is On-treatment in the Intervention Phase (as assigned based on Section 13.3). • When no HIV-1 RNA data is available within a window, a participant cannot be assigned to the category of 'HIV-1 RNA < 50 c/mL'. Depending on the reason for lack of data, the participant will be classified as 'HIV-1 RNA ≥ 50 c/mL' or reported as 'No Virologic Data at Week X'; in the latter case, the algorithm further classifies the nature of the missing data. Typically, a participant withdrawn (i) due to AE or, (ii) for another reason yet was suppressed at the time, will be counted as 'No Virologic Data at Week X'. Should a participant withdraw for reasons other than AE and was not suppressed at the time, they will be categorized as 'HIV-1 RNA ≥ 50 c/mL'. 	

Efficacy

 Full details of the algorithm, including the handling of special cases, are included in Appendix 9: Snapshot Algorithm Details.
Plasma HIV-1 RNA

 For summaries and analyses which use HIV-1 RNA level as a continuous measure, the logarithm to base 10 of the value will be used. HIV-1 RNA results may be provided as censored values, such as <40 or >9,999,999 c/mL. For the purposes of summary statistics, such values will be replaced by the next value beyond the limit of detection, e.g., 39 or 10,000,000 c/mL, respectively, for the given examples. Data listings will show the censored values as provided.
Confirmed Virologic Failure (CVF)

 For the purposes of clinical management in this study, CVF is defined as: 
 Rebound as indicated by two consecutive plasma HIV-1 RNA levels \geq 200 c/mL. The CVF definition is provided in the protocol Section 7.1.3 Only plasma HIV-1 RNA values determined by the central laboratory will be used to assess virologic failure.
CDC Classification for HIV-1 Infection (2014)

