13.7.2.2. Handling of Missing Data for Statistical Analysis

Element	Reporting Detail
Snapshot	
• In the Snapshot dataset, subjects without HIV – 1 RNA data in the assessment window for the visit of interest (due to missing data or discontinuation of IP prior to the visit window) do not belong to 'HIV-1< 50 c/mL (or 200 c/mL) The nature of this missing data will be further classified in Snapshot summaries as either 'HIV-1 RNA≥50' or 'No Virologic Data at Week X';• See Appendix 9: Snapshot Algorithm Details
LOCF (COVID-19 Related)	
• Missing HIV-1 RNA values within an analysis visit for reasons related to COVID-19 will be imputed using the last on-treatment value from earlier analysis timepoints.• This approach will be used in the primary snapshot analysis to address missing data due to COVID-19.

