13.13.5. Efficacy Tables

Efficacy: Tables					
No.	Population	GSK Standard/Example Shell	Title	Programming Notes	Deliverable
Snapshot					
2.1.	Safety	EFF_T1 See Section 13.14	Summary of Study Outcomes (50 c/mL cutoff) at Month 12 (Intervention Phase) – Modified Snapshot Analysis with COVID-19 related LOCF	Missing HIV-1 RNA due to COVID-19 are imputing using last post baseline value carried forward.	HL, M12
2.2.	Safety	EFF_T2 See Section 13.14	Summary of Study Outcomes (50 c/mL cutoff) at Month 12 (Intervention Phase) –Snapshot Analysis	With expanded COVID-19 related/Non-related categories	HL, M12
2.3.	Safety	SNAPSHOT4	Proportion of Subjects with Plasma HIV-1 RNA \geq 50 c/mL Over Time (Intervention Phase) – Modified Snapshot Analysis with COVID-19 related LOCF	Missing HIV-1 RNA due to COVID-19 are imputing using last post baseline value carried forward. Use Exact (Clopper-Pearson) method for 95% confidence Intervals.	M12

Efficacy: Tables					
No.	Population	GSK Standard/Example Shell	Title	Programming Notes	Deliverable
2.4.	Safety	SNAPSHOT4	Proportion of Subjects with Plasma HIV-1 RNA < 50 c/mL Over Time (Intervention Phase) – Modified Snapshot Analysis with COVID-19 related LOCF	Missing HIV-1 RNA due to COVID-19 are imputing using last post baseline value carried forward. Use Exact (Clopper-Pearson) method for 95% confidence Intervals.	M12
2.5.	Safety	SNAPSHOT7	Summary of Study Outcomes (50 c/mL cutoff) at Month 12 by Site Type (Intervention Phase) – Modified Snapshot Analysis with COVID-19 related LOCF	Missing HIV-1 RNA due to COVID-19 are imputing using last post baseline value carried forward.	M12
CVF					
2.6.	Safety	VF1	Cumulative Proportion of Subjects Meeting Confirmed Virologic Failure Criteria Over Time (Intervention Phase)		HL, M12
2.7.	Safety	207966/primary_15/T2.23	Cumulative Proportion of Subjects Meeting Confirmed Virologic Failure Criteria Over Time		M12, EOS
CD4					
2.8.	Safety	LB1	Summary of CD4+ Cell Count (cells/mm ³) by Visit		M12, EOS
2.9.	Safety	LB1	Summary of Change from Baseline in CD4+ Cell Count (cells/mm ³) by Visit		M12, EOS

Efficacy: Tables					
No.	Population	GSK Standard/ Example Shell	Title	Programming Notes	Deliverable
HIV Associated Conditions					
2.10.	Safety	CDC2	Summary of Post-Baseline CDC Stage 3 HIV-1 Associated Conditions Including Recurrences		M12, EOS
2.11.	Safety	CDC2	Summary of Post-Baseline CDC Stage 3 HIV-1 Associated Conditions Excluding Recurrences		M12, EOS
Plasma HIV-1 RNA					

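### The FDA Snapshot is the defined endpoint at every planned visit, but before Month 12 it is displayed only in a COVID-19 LOCF version that counts some missing values as <50 c/mL

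*SAP*

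**What the plan says.** **Endpoint.** Section 7.1.1 sets the proportions <50 and ≥50 c/mL "over time using the FDA Snapshot Algorithm. See Section 13.9 for Snapshot Algorithm details". Section 7.1.4.1 says they are presented "at each planned visit with corresponding 95% confidence intervals calculated using the Clopper-Pearson exact method". Neither section mentions imputation.

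**Missing values in the algorithm.** Section 13.6.3 states: "When no HIV-1 RNA data is available within a window, a participant cannot be assigned to the category of 'HIV-1 RNA < 50 c/mL". Appendix 9, step 3.2.1.2, places an on-study participant whose value is missing because of COVID-19 under no virologic data. Step 3.2.2.2 does the same for a participant who withdrew for a COVID-19 safety reason. Appendix 9 contains no LOCF step. The only modification it describes is splitting the reason categories by COVID-19 relatedness.

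**LOCF.** Section 7.1.3 first treats as non-responders "Participants without evaluable HIV-RNA data for the visit of interest". It then says that viral loads missing for COVID-19 reasons "will be imputed using an LOCF approach in which the last on-treatment viral load value will be carried forward", and its examples include treatment discontinuation for a COVID-19 adverse event. Section 13.7.2.2 adds: "This approach will be used in the primary snapshot analysis to address missing data due to COVID-19".

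**Displays.** Tables 2.3 and 2.4 (Section 13.13.5) and Figures 2.1 and 2.2 (Section 13.13.6) are all titled "Over Time (Intervention Phase) – Modified Snapshot Analysis with COVID-19 related LOCF" and carry the Clopper-Pearson instruction. Table 2.2 gives the unmodified Snapshot at Month 12, and Listing 10 shows both outcomes at Month 12. Table 2.12 is an over-time table of <50 c/mL on observed cases, for the end-of-study delivery only.

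**The concern.** The endpoint sections promise one estimate at each visit and the display list delivers another. Before Month 12, no planned display shows the unmodified Snapshot.

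The difference has a direction for the <50 proportion. Where the last value was <50, carrying it forward turns a no-data outcome into a success. The exact interval then treats that imputed success as an observation.

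The discontinuation example in Section 7.1.3 goes further. Read literally, a suppressed participant who stopped treatment for a COVID-19 adverse event would be carried as <50 at later visits with no stated limit. That is more than bridging a missed visit, and it contradicts step 3.2.2.2.

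At stake is whether a reader can see the endpoint as defined at the visits before Month 12, and how much of each reported proportion is imputed. No hypothesis is tested (Section 2.4), so no error rate is affected.

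**Working it through.** The SAP gives no response rate or sample-size calculation for this endpoint, so there is no stated figure to reproduce. The check sets the text against the display list and then sizes the shift.

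**1. Which displays use which algorithm**

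| Display | Timing | Version |
|---|---|---|
| Tables 2.3, 2.4 | Over time | Snapshot with COVID-19 LOCF |
| Figures 2.1, 2.2 | Over time | Snapshot with COVID-19 LOCF |
| Tables 2.1, 2.5; Figure 2.3 | Month 12 | Snapshot with COVID-19 LOCF |
| Table 2.2 | Month 12 | Unmodified Snapshot |
| Listing 10 | Month 12 | Both |
| Table 2.12 | Over time, end of study | Observed case, <50 only |

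Four of four over-time Snapshot displays use LOCF and none uses the unmodified algorithm. Table 2.12 does not fill the gap: it is not a Snapshot analysis and does not cover ≥50.

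**2. One participant under each rule.** Take a participant <50 at Month 4, still on study, with no sample in the Month 6 window for a COVID-19 reason. Section 13.6.3 and step 3.2.1.2 give no virologic data. Section 7.1.3 and the note to Table 2.4 give <50.

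**3. Shift in the <50 proportion.** With N = 115 (Section 2.3) and k COVID-missing participants last <50, the shift is k/115, or 1/115 = 0.87 points each.

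Illustration, assuming 5 participants are not <50 for non-COVID reasons. The LOCF proportion is then (115 − 5)/115 = 110/115 = 95.7% (95% Clopper-Pearson 90.1 to 98.6) whatever k is. The unmodified proportion is (110 − k)/115:

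| k (assumed) | Unmodified <50 | 95% CI | Gap |
|---|---|---|---|
| 2 | 108/115 = 93.9% | 87.9 to 97.5 | 2/115 = 1.7 points |
| 5 | 105/115 = 91.3% | 84.6 to 95.8 | 5/115 = 4.3 points |
| 10 | 100/115 = 87.0% | 79.4 to 92.5 | 10/115 = 8.7 points |
| 15 | 95/115 = 82.6% | 74.4 to 89.0 | 15/115 = 13.0 points |

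The SAP supplies neither k nor the 5. Only the 0.87 points per participant rests on it.

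**4. The ≥50 proportion.** Without LOCF, an on-study COVID-missing participant is not in the ≥50 row. Carrying a value <50 leaves that row unchanged, and carrying a value ≥50 adds to it. If 2 others are ≥50 and one carried value is ≥50, the row moves from 2/115 = 1.7% to 3/115 = 2.6%. LOCF is neutral or conservative here.

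**5. The carried value.** Sections 7.1.3 and 13.7.2.2 carry the last on-treatment value. The notes to the LOCF tables and to Figures 2.1 and 2.2 carry the last post-baseline value. These can differ once treatment has stopped: a rebound measured after the on-treatment period would be carried under the display note but ignored under Section 7.1.3.

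**The case against.** The strongest reply is that LOCF is a declared choice. Section 7.1.3 is the intercurrent-event strategy for this endpoint, Section 13.7.2.2 gives LOCF primary status, and all four displays name it in their titles. On this view Section 13.6.3 and Appendix 9 describe the base algorithm, which Table 2.2 reports at the primary timepoint with COVID-19 reasons separated. This stands: a reader might infer a hidden departure from the plan, and the documents do not support that.

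Other limits also stand:

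- A reader might infer that every over-time display is imputed. The virologic failure tables (2.6 and 2.7) carry no LOCF note, and Table 2.12 is observed case.
- A reader might infer that all missing data count as success. Only COVID-19-related gaps are imputed, a carried value may be ≥50, and other gaps stay as no virologic data.
- Windows before Month 12 are wide (about one and a half to two months from Month 2 to Month 10) and accept unscheduled samples. One missed visit need not leave a window empty.
- The shell for Table 2.2 is not shown, so nothing follows about whether it has intervals.
- The endpoint is secondary in a descriptive implementation study.

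None of this supplies an unmodified over-time result, and none aligns Sections 7.1.1 and 7.1.4.1 with Sections 7.1.3 and 13.7.2.2.

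**Conclusion.** The point holds as an inconsistency and a missing set of displays. The endpoint sections name the FDA Snapshot without qualification, the missing-data sections make COVID-19 LOCF primary, and before Month 12 only the LOCF version is displayed. For the <50 proportion, each COVID-missing participant last <50 adds 0.87 points at N = 115. The total depends on a count that the SAP does not give, and the ≥50 proportion is not lowered for on-study participants.

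A reader might go further and conclude that the stated endpoint is never produced, or that LOCF must be demoted to a sensitivity analysis. The first is too strong, because the unmodified Snapshot is planned at Month 12 and LOCF is prespecified. The second is a debatable preference that the documents do not compel. The conclusion also rests on reading the discontinuation example in Section 7.1.3 literally. If the sponsor did not intend to carry values forward after a COVID-19 discontinuation, the text should say so.

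**What to change.** 1. Add unmodified-Snapshot versions of Tables 2.3 and 2.4 and Figures 2.1 and 2.2, with Clopper-Pearson intervals, beside the LOCF versions.
2. Show at each visit the number of participants whose value was imputed.
3. Name the LOCF modification in Sections 7.1.1 and 7.1.4.1 and state which version is the endpoint. Cross-refer from Section 13.6.3 and Appendix 9.
4. Use one definition of the carried value in Sections 7.1.3 and 13.7.2.2 and the display notes. State whether it applies after discontinuation for a COVID-19 adverse event, and reconcile this with step 3.2.2.2.

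The cost is SAP wording and up to four repeated displays, using the algorithm already needed for Table 2.2. The additional <50 proportions may look slightly less favourable than the LOCF ones.

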13.13.6. Efficacy Figures

Efficacy: Figures					
No.	Population	GSK Standard / Example Shell	Title	Programming Notes	Deliverable
2.1.	Safety	SNAPSHOT8	Percent (95% CI) of Subjects with Plasma HIV-1 RNA \geq 50 copies/mL Over Time (Intervention Phase) – Modified Snapshot Analysis with COVID-19 related LOCF	Missing HIV-1 RNA due to COVID-19 are imputing using last post baseline value carried forward. Use Exact (Clopper-Pearson) method for 95% confidence Intervals.	M12
2.2.	Safety	SNAPSHOT8	Percent (95% CI) of Subjects with Plasma HIV-1 RNA $<$ 50 copies/mL Over Time (Intervention Phase) – Modified Snapshot Analysis with COVID-19 related LOCF	Missing HIV-1 RNA due to COVID-19 are imputing using last post baseline value carried forward. Use Exact (Clopper-Pearson) method for 95% confidence Intervals.	M12

Efficacy: Figures					
No.	Population	GSK Standard / Example Shell	Title	Programming Notes	Deliverable
2.3.	Safety	SNAPSHOT10	Individual Plasma HIV-1 RNA for Subjects Snapshot Algorithm Plasma HIV-1 RNA >= 50 copies/mL at Month 12 – Modified Snapshot Analysis with COVID-19 related LOCF	The 1st vertical line indicates start of study treatment at Intervention Phase. The second vertical reference line indicates last IP on-treatment study day. i.e. min (last IP injection dose+35 days, LTFU HAART start date, date of last oral CAB+RPV+1). This vertical line is only for subjects who withdraw from Intervention Phase/Extension phase.	M12

Efficacy: Figures					
No.	Population	GSK Standard / Example Shell	Title	Programming Notes	Deliverable
2.4.	Safety	SNAPSHOT10	Individual Plasma HIV-1 RNA for Subjects with Confirmed Virologic Failure	The 1st vertical line indicates start of study treatment at Intervention Phase. The second vertical reference line indicates last IP on-treatment study day. i.e. min (last IP injection dose+35 days, LTFU HAART start date, date of last oral CAB+RPV+1). This vertical line is only for subjects who withdraw from Intervention Phase/Extension phase. Include all plasma HIV-1 RNA data for a subject.	M12, EOS

13.13.7. Safety Tables

Note: The summary table for individual AESI may be added or removed per final AESI list for the analysis.

Safety: Tables					
No.	Population	GSK Standard/ Example Shell	Title	Programming Notes	Deliverable
Exposure					
3.1.	Safety	207966/primary_15/T3.1	Summary of Exposure to Study Treatment (Intervention Phase)		M12
3.2.	Safety	207966/primary_15/T3.1	Summary of Exposure to Study Treatment		M12, EOS
3.3.	Safety	SAF_T1 See Section 13.14	Summary of Adherence to CAB LA + RPV LA Dosing Schedule by Visit, Site Type and COVID-19 Impact /Non-Impact (Intervention Phase)	COVID Impact refers to missed or out of window injections for COVID-19 related reasons (as captured as COVID-19 related protocol deviations)	HL, M12
3.4.	Safety	SAF_T2 See Section 13.14	Summary of Adherence to CAB LA + RPV LA Dosing Schedule by Visit, Site ID and COVID-19 Impact /Non-Impact (Intervention Phase)	COVID Impact refers to missed or out of window injections for COVID-19 related reasons (as captured as COVID-19 related protocol deviations)	HL, M12

Safety: Tables					
No.	Population	GSK Standard/Example Shell	Title	Programming Notes	Deliverable
3.5.	Safety	SAF_T1 See Section 13.14	Summary of Adherence to CAB LA + RPV LA Dosing Schedule by Visit, Site Type and COVID-19 Impact /Non-Impact	COVID Impact refers to missed or out of window injections for COVID-19 related reasons (as captured as COVID-19 related protocol deviations)	EOS
3.6.	Safety	SAF_T2 See Section 13.14	Summary of Adherence to CAB LA + RPV LA Dosing Schedule by Visit, Site ID and COVID-19 Impact /Non-Impact	COVID Impact refers to missed or out of window injections for COVID-19 related reasons (as captured as COVID-19 related protocol deviations)	EOS
Adverse Events (AEs)					
3.7.	Safety	AE3	Summary of Adverse Events by Overall Frequency	ICH E3	M12, EOS
3.8.	Safety	AE5B	Summary of Adverse Events by System Organ Class and Maximum Grade	ICH E3	HL, M12, EOS
3.9.	Safety	AE5B	Summary of Adverse Events by System Organ Class and Maximum Grade — Excluding Study Drug Injection Site Reactions		M12, EOS
3.10.	Safety	AE5B	Summary of Adverse Events by System Organ Class and Maximum Grade (Oral Lead-in Period)		M12
3.11.	Safety	AE3	Summary of Common (>=5%) Adverse Events by Overall Frequency	ICH E3	M12, EOS

Safety: Tables					
No.	Population	GSK Standard/ Example Shell	Title	Programming Notes	Deliverable
3.12.	Safety	AE3	Summary of Common (>=1%) Grade 2-5 Adverse Events by Overall Frequency	ICH E3	M12, EOS
3.13.	Safety	AE3	Summary Drug-Related Adverse Events by Overall Frequency	ICH E3	M12, EOS
3.14.	Safety	AE5B	Summary of Drug-Related Adverse Events by System Organ Class and Maximum Grade	ICH E3	HL, M12, EOS
3.15.	Safety	AE5B	Summary of Drug-Related Adverse Events by System Organ Class and Maximum Grade — Excluding Study Drug Injection Site Reactions		M12, EOS
3.16.	Safety	AE15	Summary of Common (>=5%) Non-serious Adverse Events by System Organ Class and Preferred Term (Number of Subjects and Occurrences)	FDAAA, EudraCT	M12, EOS
3.17.	Safety	AE3	Summary of Common (>=1%) Drug-Related Grade 2-5 Adverse Events by Overall Frequency	ICH E3	M12, EOS
3.18.	Safety	AE3	Summary of Non-Serious Drug-Related Adverse Events by Overall Frequency	Plain Language Summary requirements.	M12, EOS

Safety: Tables					
No.	Population	GSK Standard/ Example Shell	Title	Programming Notes	Deliverable
Serious and Other Significant Adverse Events					
3.19.	Safety	AE5B	Summary of Serious Adverse Events by System Organ Class and Maximum Grade	ICH E3	HL, M12, EOS
3.20.	Safety	AE16	Summary of Serious Adverse Events by System Organ Class and Preferred Term (Number of Subjects and Occurrences)	FDAAA, EudraCT	M12, EOS
3.21.	Safety	AE1	Summary of Adverse Events Leading to Permanent Discontinuation of Study Treatment or Withdrawal from Study by System Organ Class and Preferred Term	GSK Statistical Display Standard	HL, M12, EOS
3.22.	Safety	AE20	Summary of Serious Fatal and Non-Fatal Drug-Related Adverse Events by Overall Frequency	Plain Language Summary requirements.	M12, EOS
Injection Site Reaction Adverse Events					
3.23.	Safety	201584/primary_7/T3.40	Summary of Study Drug Injection Site Reaction Adverse Events (Event-level Summary)		HL, M12, EOS
3.24.	Safety	201584/primary_7/T3.43	Summary of Subject-level Characteristics of Study Drug Injection Site Reaction Adverse Events – Overall and Common		HL, M12, EOS
3.25.	Safety	201584/primary_7/T3.46	Summary of Study Drug Injection Site Reaction Adverse Events by Visit and Maximum Severity – Overall and Common		HL, M12, EOS

Safety: Tables					
No.	Population	GSK Standard/ Example Shell	Title	Programming Notes	Deliverable
Laboratory: Chemistry					
3.26.	Safety	LB1	Summary of Chemistry Values	Includes pre-specified parameters repeated in conventional units. Includes baseline values	M12, EOS
3.27.	Safety	LB1	Summary of Chemistry Changes from Baseline	ICH E3	M12, EOS
3.28.	Safety	LB16	Summary of Chemistry Results by Maximum Grade Increase Post-Baseline Relative to Baseline	ICH E3	HL, M12, EOS
3.29.	Safety	LB16	Summary of Chemistry Results by Maximum Grade Increase Post-Baseline Relative to Baseline (Oral Lead-in Period)	ICH E3	M12
Laboratory: Hematology					
3.30.	Safety	LB1	Summary of Hematology Values	Includes pre-specified parameters repeated in conventional units.	M12, EOS
3.31.	Safety	LB1	Summary of Hematology Changes from Baseline	Includes pre-specified parameters repeated in conventional units. Includes baseline values	M12, EOS
3.32.	Safety	LB16	Summary of Hematology Results by Maximum Grade Increase Post-Baseline Relative to Baseline	ICH E3	M12, EOS

Safety: Tables					
No.	Population	GSK Standard/ Example Shell	Title	Programming Notes	Deliverable
3.33.	Safety	LB16	Summary of Hematology Results by Maximum Grade Increase Post-Baseline Relative to Baseline (Oral Lead-in Period)	ICH E3	M12
Laboratory: Hepatobiliary (Liver)					
3.34.	Safety	LIVER1	Summary of Liver Monitoring/Stopping Event Reporting	GSK Statistical Display Standard	M12, EOS
3.35.	Safety	LIVER10	Summary of Hepatobiliary Laboratory Abnormalities	GSK Statistical Display Standard	HL, M12, EOS
3.36.	Safety	LIVER11	Summary of Liver Restart/Re-Challenges	GSK Statistical Display Standard	M12, EOS
Vital Signs					
3.37.	Safety	VS1	Summary of Change from Baseline in Vital Signs	ICH E3 Include Baseline values	M12, EOS
Cardiovascular Risk Factors					
3.38.	Safety	FH1	Summary of Family History of Cardiovascular Risk Factors	GSK Statistical Display Standard	M12, EOS
3.39.	Safety	SU1	Summary of Substance Use	GSK Statistical Display Standard	M12, EOS

Safety: Tables					
No.	Population	GSK Standard/Example Shell	Title	Programming Notes	Deliverable
COVID-19 Adverse Events					
3.40.	Safety	PAN1	Summary of COVID-19 Assessments for Subjects with COVID-19 Adverse Events	GSK Statistical Display Standard, for EOS, use PAN1A shell and replace the first footnote with “[1] COVID-19 case diagnosis is based on WHO definition that was in effect at the time of diagnosis.”	M12, EOS
3.41.	Safety	PAN2	Summary of COVID-19 Additional Assessments for Subjects with COVID-19 Adverse Events	GSK Statistical Display Standard, for EOS, use PAN2A.	M12, EOS
3.42.	Safety	PAN3	Summary of COVID-19 Symptoms for Subjects with COVID-19 Adverse Events	GSK Statistical Display Standard, for EOS, use PAN3A.	M12, EOS
Adverse Events of Special Interest					
3.43.	Safety	201584/primary_27/T3.140	Summary of Depression, Anxiety and Suicidal or Suicidal Ideation/Behaviour Adverse Events by System Organ Class, Maximum DAIDS Toxicity Grade, and History of Depression, Anxiety or Suicidal Ideation/Behaviour at Screening		M12, EOS
3.44.	Safety	201584/primary_07/T3.122	Summary of Depression Adverse Events of Special Interest by System Organ Class and Preferred Term (Number of Subjects and Occurrences)		M12, EOS

Safety: Tables					
No.	Population	GSK Standard/Example Shell	Title	Programming Notes	Deliverable
3.45.	Safety	201584/primary_07/T3.125	Summary of Anxiety Adverse Events of Special Interest by System Organ Class and Preferred Term (Number of Subjects and Occurrences)		M12, EOS
3.46.	Safety	201584/primary_07/T3.128	Summary of Suicidal Ideation/Behaviour Adverse Events of Special Interest by System Organ Class and Preferred Term (Number of Subjects and Occurrences)		M12, EOS
3.47.	Safety	201584/primary_07/T3.134	Summary of Seizures Adverse Events of Special Interest by System Organ Class and Preferred Term (Number of Subjects and Occurrences)		M12, EOS
3.48.	Safety	201584/primary_07/T3.137	Summary of Hepatic Safety Profile: Assessment of Risk of Hepatotoxicity Adverse Events of Special Interest by System Organ Class and Preferred Term (Number of Subjects and Occurrences)		M12, EOS
3.49.	Safety	201584/primary_07/T3.140	Summary of Hypersensitivity Reactions (HSR) Adverse Events of Special Interest by System Organ Class and Preferred Term (Number of Subjects and Occurrences)		M12, EOS
3.50.	Safety	201584/primary_07/T3.143	Summary of Rash Adverse Events of Special Interest by System Organ Class and Preferred Term (Number of Subjects and Occurrences)		M12, EOS
3.51.	Safety	201584/primary_07/T3.146	Summary of Prolongation of the Corrected QT Interval of the ECG in Supratherapeutic Doses Adverse Events of Special Interest by System Organ Class and Preferred Term (Number of Subjects and Occurrences)		M12, EOS

Safety: Tables					
No.	Population	GSK Standard/Example Shell	Title	Programming Notes	Deliverable
3.52.	Safety	201584/primary_07/T3.149	Summary of Bipolar Disorder Adverse Events of Special Interest by System Organ Class and Preferred Term (Number of Subjects and Occurrences)		M12, EOS
3.53.	Safety	201584/primary_07/T3.152	Summary of Psychosis Adverse Events of Special Interest by System Organ Class and Preferred Term (Number of Subjects and Occurrences)		M12, EOS
3.54.	Safety	201584/primary_07/T3.155	Summary of Mood Disorders Adverse Events of Special Interest by System Organ Class and Preferred Term (Number of Subjects and Occurrences)		M12, EOS
3.55.	Safety	201584/primary_07/T3.158	Summary of Sleep Disorders Adverse Events of Special Interest by System Organ Class and Preferred Term (Number of Subjects and Occurrences)		M12, EOS
3.56.	Safety	201584/primary_07/T3.161	Summary of Hyperglycaemia Adverse Events of Special Interest by System Organ Class and Preferred Term (Number of Subjects and Occurrences)		M12, EOS
3.57.	Safety	201584/primary_07/T3.161	Summary of Weight Gain Adverse Events of Special Interest by System Organ Class and Preferred Term (Number of Subjects and Occurrences)		M12, EOS
3.58.	Safety	201584/primary_07/T3.164	Summary of Rhabdomyolysis Adverse Events of Special Interest by System Organ Class and Preferred Term (Number of Subjects and Occurrences)		M12, EOS

Safety: Tables					
No.	Population	GSK Standard/Example Shell	Title	Programming Notes	Deliverable
3.59.	Safety	201584/primary_07/T3.167	Summary of Pancreatitis Adverse Events of Special Interest by System Organ Class and Preferred Term (Number of Subjects and Occurrences)		M12, EOS
3.60.	Safety	201584/primary_07/T3.170	Summary of Impact on Creatinine Adverse Events of Special Interest by System Organ Class and Preferred Term (Number of Subjects and Occurrences)		M12, EOS
3.61.	Safety	201584/primary_07/T3.173	Summary of Safety in Pregnancy Adverse Events of Special Interest by System Organ Class and Preferred Term (Number of Subjects and Occurrences)		M12, EOS
3.62.	Safety	207966/primary_15/T3.109	Summary of Characteristics of Adverse Events of Special Interest		M12, EOS

